### **8.1. Pharmacodynamic Assessments**

Planned time points for all pharmacodynamic assessments are provided in the Schedule of Study Procedures ([Table 1](#)).

#### **8.1.1. Cardiac Biomarkers**

[figure not shown]
Blood samples will be collected to evaluate NT-proBNP, hs-cTnT, [REDACTED] concentrations as outlined in [Table 1](#).

With the exception of post-exercise cardiac biomarker samples, where indicated in the Schedule of Study Procedures, all blood draws for cardiac biomarkers must be drawn at rest and prior to exercise. Unscheduled or additional blood samples may be collected if appropriate in the opinion of the investigator (eg, for medical management of heart failure) and/or MyoKardia or their designee. Whenever possible, discussion with the study medical monitor is encouraged.

CONFIDENTIAL

Approved v2.0

## **8.2. Safety Assessments**

Planned time points for all safety assessments are provided in the Schedule of Study Procedures ([Table 1](#)).

CONFIDENTIAL

Approved v2.0

### **8.2.1. Medical History**

A complete medical history will be recorded at the Screening visit, which will include evaluation (past or present) of the following: general, head and neck, eyes, ears, nose, throat, chest/respiratory, heart/cardiovascular, gastrointestinal/liver, gynecological/urogenital, musculoskeletal/extremities, skin, neurological/psychiatric, endocrine/metabolic, hematologic/lymphatic, allergies/drug sensitivities, past surgeries, substance abuse, or any other diseases or disorders as well as participation in clinical studies (study medication and/or device or other therapy).

### **8.2.2. Physical Examinations**

At selected visits, a complete physical examination will be conducted including a neurological examination (gross motor and deep tendon reflexes), height (Prescreening and/or Screening only) and weight, and assessment of the following: general appearance, skin, head and neck, mouth, lymph nodes, thyroid, abdomen, musculoskeletal, cardiovascular, and respiratory systems. At all other clinic visits, an abbreviated cardiopulmonary physical examination will be conducted, with other systems assessed as directed by interval history.

Height (cm) and body weight (kg) will be measured at Prescreening and/or Screening, and body mass index ( $\text{kg/m}^2$ ) will be calculated. Participants will be required to remove their shoes and wear clothing as specified by the clinical site.

Body weight will be recorded as indicated in [Table 1](#).

### **8.2.3. Vital Signs**

Complete vital signs including temperature, HR, respiratory rate (RR), and BP will be assessed as in indicated in [Table 1](#).

Vital signs will be obtained with the participant in the same position; BP will be taken after at least 5 minutes of rest via an automated recorder.

At all visits, vital signs will be taken prior to dosing. Alert values will be flagged. Refer to the Study Laboratory Manual for additional details.

### **8.2.4. 12-Lead Electrocardiograms**

Central read, single 12-lead ECG evaluations will be performed after 10 minutes of rest as indicated in [Table 1](#). At clinic visits during the treatment period, ECGs will be taken prior to dosing.

The investigator may perform 12-lead ECG safety assessments if he/she considers it is required for any other safety reason. These assessments should be recorded as an unscheduled assessment.

### **8.2.5. Clinical Safety Laboratory Assessments**

Safety laboratory results will be assessed in an ongoing manner. See [Section 10.3](#) for the list of clinical laboratory tests to be performed and to the Schedule of Study Procedures ([Table 1](#)) for the timing and frequency.

- The investigator must review the laboratory report, document this review, and record any clinically significant changes occurring during the study as an AE. The laboratory reports must be filed with the source documents.

CONFIDENTIAL

Approved v2.0

- Abnormal laboratory findings associated with the underlying disease are not considered clinically significant unless judged by the investigator to be more severe than expected for the participant's condition.
- All laboratory tests considered clinically significant abnormal values during participation in the study should be repeated until the values return to normal or baseline or are no longer considered clinically significant by the investigator or study medical monitor.
  - If clinically significant values do not return to normal/baseline within a period of time judged reasonable by the investigator, the etiology should be identified, and MyoKardia or their designee notified.
  - All protocol-required laboratory tests, as defined in [Section 10.3](#), must be conducted in accordance with the laboratory manual and the Schedule of Study Procedures ([Table 1](#)).
  - If laboratory values from non-protocol specified laboratory tests performed at the institution's local laboratory require a change in participant management or are considered clinically significant by the investigator (eg, SAE or AE or dose modification), then the results must be recorded.

#### **8.2.6. Pregnancy Testing**

Serum pregnancy testing will be performed at Screening for all females of childbearing potential. In addition, urine pregnancy testing in clinic will be conducted every 4 to 6 weeks throughout the study. Confirmatory serum testing will be performed if any urine test is positive.

### **8.3. Adverse Events, Serious Adverse Events, and Other Safety Reporting**

The investigator should refer to [Section 10.4](#) for detailed definitions of AEs and SAEs and additional information regarding AE reporting.

AEs will be reported by the participant (or, when appropriate, by a caregiver, surrogate, or the participant's legally authorized representative).

The investigator and any qualified designees are responsible for detecting, documenting, and recording events that meet the definition of an AE or SAE and remain responsible for following up on all AEs.

The method of recording, evaluating, and assessing causality of AEs and SAEs and the procedures for completing and transmitting SAE reports are provided in [Section 10.4](#).

#### **8.3.1. Time Period and Frequency for Collecting AE and SAE Information**

All AEs, including SAEs, will be collected from the signing of the informed consent form (ICF) until 56 days after the last dose of study drug ([Table 1](#)).

Medical occurrences that begin before the start of study drug but after obtaining informed consent will be recorded as pretreatment adverse events (PTAEs), as detailed in [Section 10.4](#).

All SAEs/AESIs will be recorded and reported to MyoKardia or their designee immediately and under no circumstance should this exceed 24 hours, as indicated in [Section 10.4](#). The investigator will submit any updated SAE data to MyoKardia or their designee within 24 hours of it being available.

Investigators are not obligated to actively seek information on AEs or SAEs after conclusion of the study participation. However, if the investigator learns of any SAE, including a death, at any time after a participant has been discharged from the study, and he/she considers the event to be reasonably related to the study drug or study participation, the investigator must promptly notify MyoKardia or their designee (via paper SAE form).

### **8.3.2. Method of Detecting AEs and SAEs**

Care will be taken not to introduce bias when detecting AEs and/or SAEs. Open-ended and nonleading verbal questioning of the participant is the preferred method to inquire about AE occurrences.

### **8.3.3. Follow-up of AEs and SAEs**

After the initial AE/SAE report, the investigator is required to proactively follow each participant at subsequent visits/contacts. All SAEs, AESIs (as defined in [Section 8.3.6](#)), and AEs will be followed until resolution, stabilization, the event is otherwise explained, or the participant is lost to follow-up (as defined in [Section 7.3](#)), including being considered lost to follow-up at the end of the study. Further information on follow-up procedures is provided in [Section 10.4](#).

### **8.3.4. Regulatory Reporting Requirements for SAEs**

Prompt notification by the investigator to MyoKardia or their designee of an SAE is essential so that legal obligations and ethical responsibilities towards the safety of participants and the safety of a study drug under clinical investigation are met. All SAEs occurring during the treatment-emergent period (defined as the period from the first dose of study drug to the last dose of study drug + 56 days), regardless of causality, will be reported by the investigator or designee to MyoKardia or their designee within 24 hours of knowledge of the event or sequelae. Deaths and SAEs occurring after the treatment-emergent period and considered related to study drug or study procedure must also be reported. SAE reporting instructions are provided in the Study Reference Manual.

Medical records may be requested to support documentation of an SAE. The investigator is responsible for summarizing the pertinent aspects of the event (including discharge summaries, diagnostic procedures, laboratory data, and interventions) and for updating the SAE eCRF with this information.

MyoKardia or their designee retains the right to request additional information for any participant with any ongoing AEs/SAEs at the end of the study, if judged necessary.

Spontaneously reported SAEs that are considered related to study drug after completion of the study should be promptly reported by the investigator to MyoKardia or their designee.

Prompt notification by the investigator to MyoKardia or their designee of SAEs is essential so that legal obligations and ethical responsibilities for the safety of participants and the safety of a study intervention under clinical investigation are met. MyoKardia or their designee has a legal responsibility to notify both the local regulatory authority and other regulatory agencies about

the safety of a study drug under clinical investigation. MyoKardia or their designee will comply with country-specific regulatory requirements relating to safety reporting to the regulatory authority, institutional review boards (IRBs)/independent ethics committees (IECs), and investigators.

An investigator who receives an investigator safety report describing an SAE or other specific safety information (eg, summary or listing of SAEs) from MyoKardia or their designee will review and then file it along with the IB and will notify the IRB/IEC, if appropriate according to local requirements.

### **8.3.5. Pregnancy**

Female participants of childbearing potential must use appropriate methods of contraception as listed in the inclusion criteria ([Section 5.1](#)). Female participants of nonchildbearing potential are defined as those who are permanently (surgically) sterilized or are postmenopausal. Permanent sterilization includes hysterectomy, bilateral oophorectomy, and bilateral tubal occlusion or ligation. Female participants are considered postmenopausal if they have had amenorrhea for at least 1 year following cessation of all exogenous hormonal treatments and FSH levels are in the postmenopausal range.

- All pregnancies in female participants and female partners of male participants who received at least one dose of study drug must be reported if they occur anytime from the first dose of study drug to 4 months after the last dose of study drug.
- The investigator is responsible for informing MyoKardia or their designee within 24 hours of knowledge of the pregnancy even if no AE has occurred. If a pregnancy is reported, the investigator will record pregnancy information on the appropriate form and submit it to MyoKardia or their designee within 24 hours of learning of the pregnancy of the female participant or the female partner of a male participant (after obtaining the necessary signed informed consent from the female partner).
- While pregnancy itself is not considered to be an AE or SAE, any pregnancy complication or elective termination of a pregnancy for medical reasons will be reported as an AE or SAE.
- Abnormal pregnancy outcomes (eg, spontaneous abortion, fetal death, stillbirth, congenital anomalies, or ectopic pregnancy) are considered SAEs and will be reported as such.
- The participant or pregnant female partner of a male participant will be followed to determine the outcome of the pregnancy. The participant will be asked to provide information on the outcome of the pregnancy through 6 months after birth or details of premature termination of the pregnancy. The investigator will collect follow-up information on the participant or pregnant female partner of a male participant and the neonate for 6 months after birth and the information will be forwarded to MyoKardia or their designee
- Any post-study pregnancy-related SAE considered reasonably related to the study drug by the investigator will be reported to MyoKardia or their designee, as described in [Section 8.3.4](#). While the investigator is not obligated to actively seek this

CONFIDENTIAL

Approved v2.0

information in former study participants or pregnant female partners of male participants, he/she may learn of an SAE through spontaneous reporting.

- Any female participant who becomes pregnant while participating in the study will discontinue study drug.

### **8.3.6. Adverse Events of Special Interest**

Symptomatic overdose, teratogenicity, and LVEF  $\leq 30\%$  as determined by local site read or centrally read echocardiogram are considered AESIs.

AESIs are required to be reported by the investigator to MyoKardia or their designee within 24 hours, irrespective of regulatory seriousness criteria. If a participant should experience symptomatic overdose, LVEF  $\leq 30\%$ , or if pregnancy outcome becomes known, the investigator will report the information to the study medical monitor and complete the required information in the EDC system within 24 hours of study staff becoming aware of the AESI.

CONFIDENTIAL

Approved v2.0

## 9. STATISTICAL CONSIDERATIONS

### 9.1. Statistical Hypotheses

There is no formal statistical hypothesis testing in this exploratory Phase 2a study.

### 9.2. Sample Size Determination

Given the exploratory nature of the study, no formal sample size calculation was done. The sample size will be approximately 35 participants.

### 9.3. Analysis Sets

For the purpose of analysis, the following analysis populations are defined:

**Table 4: Analysis Populations Definitions**

Analysis Population	Definition
ITT	All enrolled participants regardless of whether they receive study drug.
Safety	All enrolled participants who receive at least 1 dose of study drug, with analyses conducted by actual treatment received.

ITT = intention-to-treat; [REDACTED].

### 9.4. Statistical Analyses

The statistical analysis plan (SAP) will be finalized prior to database lock and it will include a more technical and detailed description of the statistical analyses described in this section. This section is a summary of the planned statistical analyses of the most important endpoints including primary [REDACTED] endpoints.

CONFIDENTIAL

Approved v2.0

#### **9.4.1. General Considerations**

In general, descriptive summaries will be presented at each visit. The descriptive summary for continuous variables will also be provided for the change from baseline. Summaries of continuous variables will include the number of participants, mean, standard deviation (SD), median, first quartile, third quartile, minimum, and maximum. For variables with a highly skewed distribution (eg, log-normal distribution), such as hs-cTnT and NT-proBNP, geometric mean and percent coefficient of variation will also be reported in descriptive summaries. Descriptive summaries for categorical variables will include the number and percentage of participants. Unless otherwise stated, denominators for percentages will be the number of participants in the analysis population.

#### **9.4.2. Primary Pharmacodynamic Endpoints**

The primary pharmacodynamic endpoints are the following:

- Change from baseline to Week 26 in NT-proBNP (at rest)
- Change from baseline to Week 26 in hs-cTnT (at rest), as assessed by a high-sensitivity assay

Further details for these analyses will be specified in the study SAP.

CONFIDENTIAL

Approved v2.0

Further details for these analyses will be specified in the study SAP.

#### **9.4.4. Safety Endpoints**

The safety endpoints are the following:

- Frequency and severity of treatment-emergent adverse events (TEAEs), AESIs (symptomatic overdose, teratogenicity, and LVEF  $\leq 30\%$  as determined by local site read or centrally read echocardiogram), and SAEs; laboratory abnormalities; vital sign abnormalities; and cardiac rhythm abnormalities

All safety analyses will be performed for the Safety Analysis Population using the following common rules:

- The baseline value is defined generally as the last available value before the first administration of study drug, unless specified otherwise.
- For quantitative safety parameters based on central laboratory measurements, descriptive statistics will be used to summarize results and change from baseline values by visit and treatment group; changes may be presented in shift tables or scattergrams.
- The analysis of the safety variables will be descriptive, and no hypothesis testing is planned.

The safety analysis will focus on the treatment-emergent period, which is defined as the time from the first dose of study drug to the last dose of study drug + 56 days.

##### **9.4.4.1. Adverse Events**

AEs will be mapped to system organ classes (SOC) and preferred terms (PTs) using the Medical Dictionary for Regulatory Activities (MedDRA) v23.0. AEs will be monitored during the study and the data analyzed with respect to overall incidence, as well as severity and potential relationship of AEs to study drug. AEs with onset during the treatment-emergent period (ie, TEAEs) or with an onset before the first dose of study drug that increase in severity or become serious during the treatment-emergent period will be considered TEAEs.

AE incidence tables will present the number and percentage of participants experiencing at least one TEAE by SOC, high-level group term (HLGT), high-level term (HLT), and PT in alphabetical order for each treatment group. Multiple occurrences of the same event in the same participant will be counted only once within a treatment phase. The denominator for computation of percentages is the safety population within each treatment group.

AE incidence tables will be provided for TEAEs, including all TEAEs, all treatment-emergent SAEs, all treatment-emergent treatment-related AEs, all treatment-emergent treatment-related SAEs, TEAEs by severity, and all TEAEs leading to permanent treatment discontinuation.

##### **9.4.4.1.1. Death**

The number and percent of participants who died by study period (TEAE, on-study) will be summarized for the safety population, and a listing will be provided for all events involving a participant death, if applicable.

CONFIDENTIAL

Approved v2.0

#### 9.4.4.1.2. Pregnancy

The following pregnancy summaries will be generated, if applicable:

- Number of female participants or female partners of male participants who become pregnant
- Outcomes of the pregnancies and analysis of the outcomes
- TEAEs experienced during the pregnancy by primary SOC, HGLT, HLT, and PT showing the number and percent of participants sorted by internationally agreed order of SOC and alphabetic order of HGLT, HLT, and PT

#### 9.4.4.1.3. Symptomatic Overdose

The following summaries for reports of symptomatic overdose will be generated, if applicable:

- Number of participants who experienced symptomatic overdose summarized by treatment received
- Analysis of the cause and occurrence of the symptomatic overdose
- TEAE experienced during the symptomatic overdose by primary SOC, HGLT, HLT, and PT showing the number and percent of participants sorted by internationally agreed order of SOC and alphabetic order of HGLT, HLT, and PT

#### 9.4.4.2. 12-Lead Electrocardiogram

The RR, pulse rate (PR), QRS, and QT intervals will be measured and read by a central laboratory. [REDACTED]

##### 9.4.4.2.1. Correction for Heart Rate

Corrected QT interval (QTc) will be calculated using the manually over-read QT values. Each individual ECG QT value will be corrected for HR. [REDACTED]

##### 9.4.4.2.2. ECG Numeric Variables

Heart rate, PR, QRS, and QTcF will be summarized using descriptive statistics. The change from baseline of these ECG parameters at each time point will be listed for each participant. For each time point of measurement, the changes from baseline will be summarized using descriptive statistics.

#### **9.4.4.2.3. Categorical Analysis**

The number and percentage of participants with any postdose QTcF values of >450 msec, >480 msec, and >500 msec will be summarized. Participants with QTc values >500 msec will be listed with corresponding baseline values,  $\Delta$ QTcF, and baseline and treatment HR. The incidence count and percentage of participants with a  $\Delta$ QTcF increase from baseline of >30 msec and >60 msec will be summarized.

#### **9.4.4.2.4. Morphology Findings**

New ECG morphologies for each participant not present on any ECG at baseline for that participant will be summarized for all observation time points combined.

The number and percentage of participants having T-wave morphology changes and/or the occurrence of abnormal U-waves that represent the appearance or worsening of the morphological abnormality from baseline will be reported.

#### **9.4.4.3. Laboratory Data**

The summary statistics (including number of participants, mean, median, SD, minimum and maximum) of all laboratory variables (laboratory values and changes from baseline), will be summarized at all baseline and postbaseline time points.

Listings of participants with laboratory values that are outside of the reference range will be produced.

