## 3. OBJECTIVES AND ENDPOINTS

Objectives	Endpoints
Primary	

• To evaluate the safety and tolerability of a 26-week course of mavacamten

	

• Frequency and severity of treatment-emergent adverse events (TEAEs), adverse events of special interest (AESIs) [symptomatic overdose, outcomes of pregnancy, left ventricular ejection fraction (LVEF) <math>\leq 30\%</math>], and serious adverse events (SAEs); laboratory abnormalities; vital sign abnormalities; and cardiac rhythm abnormalities

• To evaluate the effect of a 26-week course of mavacamten on N-terminal pro b-type natriuretic peptide (NT-proBNP) levels (at rest)

	

• Change from baseline to Week 26 in NT-proBNP (at rest)

• To evaluate the effect of a 26-week course of mavacamten on cardiac troponin T (cTnT) levels (at rest)

	

• Change from baseline to Week 26 in cTnT (at rest), as assessed by a high-sensitivity assay

CONFIDENTIAL

Approved v2.0

CONFIDENTIAL

Approved v2.0

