6. Has documented LVEF  $\geq 60\%$  at the Screening visit as determined by the echocardiography central laboratory and no history of prior LVEF  $\leq 45\%$  under stable conditions. If historical LVEF  $\leq 45\%$  is not consistent with recovered HFrEF medical history, the participant may be included after review of previous echocardiographic images and discussion with the study medical monitor.
7. Has maximal left ventricular wall thickness  $\geq 12$  mm *OR* documented elevated left ventricular mass index (LVMI) by 2-dimensional imaging ( $> 95$  g/m^2 if female and  $> 115$  g/m^2 if male) as determined by the echocardiography central laboratory.
8. Has adequate acoustic windows on screening resting TTE as determined by echocardiography central laboratory, to enable high likelihood of acquisition of high quality TTEs throughout the study. Echocardiographic contrast agents may be used if the image quality of unenhanced echocardiographic images is deemed inadequate and there are no contraindications to the use of contrast agents [REDACTED].
9. Has NYHA Class II or III symptoms at Screening.

CONFIDENTIAL

10. Has safety laboratory parameters (chemistry, hematology, coagulation, and urinalysis) within normal limits (according to the central laboratory reference range) at Screening; however, a participant with safety laboratory parameters outside normal limits may be included if he/she meets all of the following criteria:
  - a. The safety laboratory parameter outside normal limits is considered by the investigator to be clinically unimportant. In this case, the investigator should discuss the result in question with the study medical monitor prior to enrollment.
  - b. If there is an alanine aminotransferase (ALT) or aspartate aminotransferase (AST) result, the value must be  $<3 \times$  the upper limit of the laboratory reference range.
  - c. The body size-adjusted estimated glomerular filtration rate is  $\geq 30$  mL/min/1.73 m^2.
11. Female participants must not be pregnant or lactating and, if sexually active (and not postmenopausal or surgically sterile per the definition below), must be using one of the following highly effective birth control methods from the Screening visit through 4 months after the last dose of study drug. Male partners must also use a contraceptive (eg, barrier, condom, or vasectomy).

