#### **9.4.4.4. Vital Signs Data**

The summary statistics (including number, mean, median, SD, minimum, and maximum) of all vital sign variables (values and changes from baseline) will be summarized at all baseline and postbaseline time points.

[figure not shown]
Listings of participants with vital sign values that are outside of the reference range will be produced.

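### Laboratory and vital sign abnormalities are components of the primary safety endpoint, but the readable analysis text plans no count of participants with a new or worsened abnormality beyond those recorded as adverse events

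*Combined protocol and SAP*

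**What the plan says.** The primary safety endpoint in Section 3 (repeated in Sections 1.1 and 9.4.4) covers TEAEs, AESIs and SAEs, and then "laboratory abnormalities; vital sign abnormalities; and cardiac rhythm abnormalities".

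For laboratory data, Section 9.4.4.3 plans "The summary statistics (including number of participants, mean, median, SD, minimum and maximum) of all laboratory variables", for values and for changes from baseline, at each time point. The only output aimed at abnormal values is "Listings of participants with laboratory values that are outside of the reference range will be produced". Section 9.4.4.4 plans the same kind of summary for vital signs and "Listings of participants with vital sign values that are outside of the reference range will be produced".

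Section 9.4.4 sets common rules for all safety analyses: baseline is generally the last value before first dose, and the focus is the period from first dose to 56 days after last dose. For quantitative parameters measured by the central laboratory it adds that "changes may be presented in shift tables or scattergrams".

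Three other places matter. Inclusion criterion 10 (Section 5.1) says "a participant with safety laboratory parameters outside normal limits may be included", subject to conditions. Section 8.2.5 requires investigators to "record any clinically significant changes occurring during the study as an AE", and Section 9.4.4.1 tabulates TEAEs by number and percentage. Sections 9.4.4.2.3 and 9.4.4.2.4 plan counts and percentages of participants for QTcF limits, for QTcF increases from baseline, and for T-wave and U-wave findings that appear or worsen from baseline.

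**The concern.** The endpoint is about how often abnormalities occur. The planned output describes the distribution of each parameter and names the people who were ever outside a range. Neither gives the frequency of abnormalities that arose or worsened on treatment. A participant who entered with an out-of-range value, one who drifted just outside a limit once, and one with a new and sustained change would all appear in the same listing.

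This matters more here because there is no control arm to supply the background rate. It also matters for vital signs in particular. Section 2.3.1 says that reduced tolerance might show as changes in resting heart rate or systolic blood pressure, yet the optional shift tables do not extend to vital signs.

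**Working it through.** The plan states no sample-size calculation, power or expected abnormality rate, so there is no figure of its own to reproduce. The check has three parts.

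**1. Planned outputs side by side**

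| Component | Count of participants relative to baseline? |
|---|---|
| ECG (9.4.4.2.3, 9.4.4.2.4) | Yes: QTcF increase categories; new or worsened morphology |
| Laboratory (9.4.4, 9.4.4.3) | No; shift table optional |
| Vital signs (9.4.4.4) | No; not covered by the optional shift table |

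**2. How many participants the laboratory listing would name by chance**

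Inputs from the protocol:
- Table 5 gives 13 hematology + 2 coagulation + 16 chemistry = 31 numeric tests (urinalysis left out).
- Section 4.1 gives seven post-baseline clinic visits: Weeks 6, 12, 14, 18, 22, 26 and 34.
- N is about 35.

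Assumed, because the documents do not give it: a share *a* of values lies outside the range with no drug effect, with *a* = 1%, 2.5% or 5%.

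With independent tests, P(at least one out of range) = 1 − (1 − a)^31 at one visit. Over seven independent visits the exponent is 31 × 7 = 217.

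| a | One visit | of 35 | Seven independent visits | of 35 |
|---|---|---|---|---|
| 5% | 1 − 0.95^31 = 79.6% | 27.9 | >99.9% | 35.0 |
| 2.5% | 1 − 0.975^31 = 54.4% | 19.0 | 99.6% | 34.9 |
| 1% | 1 − 0.99^31 = 26.8% | 9.4 | 88.7% | 31.0 |

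If a participant's values were perfectly correlated across visits, the one-visit column would apply to the whole study.

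Independence is generous, so it was relaxed by simulation: normally distributed values, 5% out of range, no drug effect, correlation between tests of 0 to 0.5 and between visits of 0.5 to 0.9. At one visit the share listed falls from about 80% to about 67% (between-test correlation 0.3) and 51% (0.5). Over seven visits it is 82% to nearly 100%. Among participants whose tests were all normal at baseline, it is 66% to nearly 100% over seven visits. Abnormalities admitted under criterion 10 would add to these figures.

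**3. What a baseline-referenced count would show with no drug effect**

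Same model, one test at a time: in range at baseline and out of range at any of seven later visits.

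| Visit-to-visit correlation | Newly abnormal, one test | of 35 |
|---|---|---|
| 0.5 | 20.0% | 7.0 |
| 0.7 | 14.1% | 4.9 |
| 0.9 | 6.9% | 2.4 |

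Pooled over all 31 tests, at least one new abnormality occurs in about 73% to nearly 100% of participants. A pooled count would therefore be little better than the listing. Per-test counts are readable, though across 31 tests chance still produces about 31 × 2.4 = 74 to 31 × 7.0 = 217 participant-by-test events. That is why prespecified categories are preferable to a bare in-or-out rule.

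**The case against.** The strongest reply is that the protocol already does more than a quick reading of 9.4.4.3 suggests, and much of that reply stands.

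- A reader might infer that the safety output has no baseline and no time window. It has both: the common rules in 9.4.4 apply to all safety analyses. What is missing is a count that uses them.
- A reader might infer that a few large changes would be lost in a mean. Sections 9.4.4.3 and 9.4.4.4 also report the minimum and maximum, for changes from baseline as well as for values, so an extreme change would show.
- A reader might infer that these components have no count at all. Clinically significant laboratory changes become AEs under 8.2.5 and enter the TEAE tables, and Section 10.4.1.2 allows a sign such as tachycardia to be an AE. But this count passes through the investigator's judgement in an open-label study, and findings attributed to the underlying disease are left out unless worse than expected. The endpoint also names abnormalities separately from TEAEs.
- A reader might infer that Section 8.2.3, where "Alert values will be flagged", conflicts with the reference range in 9.4.4.4. The first is a procedural instruction; neither section defines an abnormality, so there is no contradiction. One definition is simply needed.

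Two limits on the evidence also stand. Section 9.4 defers detail to a SAP whose text was not available, and the liver subsection (9.4.4.3.1), covering four of the 31 tests, is redacted. Finally, this is a descriptive study of about 35 participants with an independent data monitoring committee, so a listing can be read person by person. That makes the gap less serious, but it does not produce a frequency.

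**Conclusion.** The point holds for the readable protocol. Two components of the primary safety endpoint have descriptive statistics and listings, but no committed number or percentage of participants with a new or worsened abnormality, apart from changes recorded as AEs. The optional shift tables would partly close the gap for laboratory data and not at all for vital signs.

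The laboratory listing cannot stand in for that frequency. The size of the chance effect rests on the assumed out-of-range rate and on correlation. To say flatly that most participants would be listed goes too far: at a 1% rate and a single visit the figure is 27%. Nor can the statement be carried over to vital signs, for which the readable text gives no range.

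This is a cheap improvement to the reporting of safety. It does not show that the plan would miss a safety signal.

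**What to change.** - **Section 9.4.4:** replace the optional wording with a planned shift table from baseline to worst post-baseline value, and extend it to vital signs.
- **Sections 9.4.4.3 and 9.4.4.4:** add, per parameter and direction (low or high), the number and percentage of Safety Population participants with a treatment-emergent abnormality. Define this as in range at baseline and out of range during the treatment-emergent period, or worsened from baseline by a prespecified category.
- **Denominator:** participants with a baseline and at least one post-baseline value. This must be written down, because the default in 9.4.1 is the whole analysis population.
- **SAP:** state the laboratory categories and a single vital sign abnormality criterion. Do not pool across tests.
- **Listing:** keep it as support and add a column for baseline status.

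If the SAP already contains these tables, only the protocol wording needs aligning. The cost is SAP text and standard table shells, with no new data. The downside is a few more tables, and some chance abnormalities per test that cannot be separated from a drug effect without a control arm.
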